7.1.8 Simplified Disease Activity Index

The SDAI will not be calculated by the Investigator during the course of the study, but will be computed in the statistical database for analysis purposes.

The SDAI will be calculated using the SJC (28 joints), TJC (28 joints), CRP (mg/dL), the Patient Global Assessment of Disease Activity (VAS) (in cm), and the Physician Global Assessment (VAS) (in cm) according to the following formula:

$$\text{SDAI} = \text{SJC} + \text{TJC} + \text{Patient Global Assessment of Disease Activity (VAS)} + \text{Physician Global Assessment (VAS)} + \text{CRP}$$

7.1.9 Clinical Disease Activity Index

The CDAI will not be calculated by the Investigator during the course of the study, but will be computed in the statistical database for analysis purposes.

The CDAI will be calculated using the SJC (28 joints), TJC (28 joints), the Patient Global Assessment of Disease Activity (VAS) (in cm), and the Physician Global Assessment (VAS) (in cm) according to the following formula:

$$\text{CDAI} = \text{SJC} + \text{TJC} + \text{Patient Global Assessment of Disease Activity (VAS)} + \text{Physician Global Assessment (VAS)}.$$

7.1.10 Health Assessments and Patient-Reported Outcomes

The PROs that will be utilized for efficacy assessments are discussed in this section.

7.1.10.1 Health Assessment Questionnaire – Disability Index

The HAQ-DI is a patient-reported questionnaire that provides an assessment of the impact of the disease and its treatment on physical function. The HAQ-DI assesses the degree of difficulty experienced in 8 domains of daily living activities using 20 questions. The domains are dressing and grooming, arising, eating, walking, hygiene, reach, grip and common daily activities, and each domain (activity) consists of 2 or 3 items. For each question, the level of difficulty is scored from 0 to 3 where 0 = without any difficulty, 1 = with some difficulty, 2 = much difficulty, and 3 = unable to do. Each category is given a score by taking the maximum score of each question (i.e., question in each category with the highest score for that category).

If the maximum score is 0 or 1, but a device related to that category is used, or help from another person is provided for the category, then the category score is increased to 2. If the category score is already a 2 (or above), the score in that category remains 2 with or without any aids or device use. If the subject does not provide an answer for any questions within a category, no score will be provided for that category. The HAQ-DI will be calculated by dividing the sum of the category scores by the number of categories with at least 1 question answered. If fewer than 6 categories have responses, no disability score will be calculated.

The HAQ-DI will also include patient assessments of pain and health on a scale of 0 to 100.

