4.2 Secondary Efficacy Endpoints

The following secondary efficacy endpoints will be evaluated:

- Percentage of subjects achieving low disease activity, defined as DAS28 (CRP) <3.2, and remaining on randomized treatment and in the study at Week 12
- Improvement of physical ability from baseline to Week 12, as measured by the Health Assessment Questionnaire-Disability Index (HAQ-DI)
- Percentage of subjects achieving an ACR50 response and remaining on randomized treatment and in the study at Week 24
- Percentage of subjects with Clinical Disease Activity Index (CDAI) ≤ 2.8 (remission) and remaining on randomized treatment and in the study at Week 24

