7. EFFICACY, SAFETY, PHARMACOKINETIC, AND HEALTH OUTCOME ASSESSMENTS

7.1 Efficacy Assessments

7.1.1 American College of Rheumatology 20%/50%/70% Response Criteria

ACR20/ACR50/ACR70 will not be calculated by the Investigator during the course of the study, but will be computed in the statistical database for analysis purposes.

The number of subjects who achieve an ACR20, ACR50, or ACR70 response at various time points will be calculated for OKZ and placebo. The calculations are based on a $\geq 20\%$, $\geq 50\%$, and $\geq 70\%$ improvement from baseline in the SJC assessed in 66 joints and in the TJC assessed in 68 joints; and a $\geq 20\%$, $\geq 50\%$, and $\geq 70\%$ improvement from baseline in at least 3 of the 5 remaining core set measures:

- Patient Global Assessment of Disease Activity (VAS).
- Patient Assessment of Pain (VAS).
- HAQ-DI.
- Physician Global Assessment (VAS).
- Level of acute phase reactant (CRP or ESR, using level of CRP in this study).

7.1.2 66-68 Joint Assessment

The 66-68 joint assessment evaluates 66 joints for swelling and 68 joints for tenderness and pain on motion. The hip joints can be assessed for tenderness, but not for swelling. The following joints are included:

- Temporomandibular, sternoclavicular, acromioclavicular, shoulders, elbows, wrists, interphalangeal (IP) on digit 1, distal interphalangeals on digits 2 to 5, proximal interphalangeals (PIP) on digits 2 to 5, metacarpophalangeal (MCP) on digits 1 to 5, hips (tenderness only), knees, ankles and tarsus; metatarsals, IP on toe 1, PIP on toes 2 to 5, and metatarsophalangeals (MTP) on toes 1 to 5.

As noted in Table 1 and Table 2, the joint assessor will be independent to the rest of the study team. An independent joint assessor, blinded to other study assessments as well as the dosing regimen, will be identified at each study site to perform the SJC and TJC. To ensure consistent joint evaluation throughout the study, individual subjects should be evaluated by the same joint assessor for all study visits, whenever possible.

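### The HAQ-DI scoring rule, as written, turns every category score of 3 into a 2, capping the index at 2.0 and hiding 3-to-2 improvements in a confirmatory secondary endpoint and an ACR component

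*Combined protocol and SAP*

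**What the plan says.** Section 7.1.10.1 builds the HAQ-DI in four steps.

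- **Items.** There are "8 domains of daily living activities using 20 questions", and "the level of difficulty is scored from 0 to 3 where 0 = without any difficulty". The upper end of the scale is "2 = much difficulty, and 3 = unable to do".
- **Category score.** "Each category is given a score by taking the maximum score of each question", meaning the highest item score in the category.
- **Aids and help.** If the category maximum is 0 or 1 and a device or another person's help is used, "then the category score is increased to 2". For higher scores: "If the category score is already a 2 (or above), the score in that category remains 2 with or without any aids".
- **Index.** The category scores are summed and divided by the number of categories answered. At least 6 categories are required.

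The index is then used in several places:

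- Section 4.2 lists "Improvement of physical ability from baseline to Week 12, as measured by the Health Assessment Questionnaire-Disability Index (HAQ-DI") as the second secondary endpoint.
- Section 7.1.1 makes it one of the ACR measures, with response requiring "improvement from baseline in at least 3 of the 5 remaining core set measures" on top of both joint counts.
- Section 4.3 defines a responder endpoint at an improvement of 0.22 or more.
- Section 9.4.9.2 plans a responder curve on percent HAQ-DI improvement.

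**The concern.** The aids rule contradicts the scale defined a few lines above it. The parenthesis in the last aids sentence can only refer to a score of 3, and the sentence applies whether or not aids are used. The only value it gives for such a category is 2. A programmer who follows it would truncate every 3, including those of subjects who use no aids at all.

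Three things are at stake.

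- **The testing sequence.** Under section 9.4.6, testing for a regimen stops at the first hypothesis not rejected at 1-sided 0.0125. HAQ-DI comes after ACR20 and DAS28 low disease activity, so ACR50 and CDAI remission at Week 24 can be tested only if HAQ-DI succeeds. Truncation weakens that link.
- **The primary endpoint.** HAQ-DI feeds ACR20, so the component can be misclassified.
- **The most disabled subjects.** Improvement from inability to much difficulty would not register, nor would worsening from 2 to 3. Such scores are to be expected: section 5.3.2 excludes only Steinbrocker class IV, so class III subjects, whose self-care or usual work is largely lost (Appendix 1), remain eligible.

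**Working it through.** The plan states no HAQ-DI score maximum, effect size, standard deviation or power (section 9.1 powers only ACR20 and DAS28), so there is no HAQ-DI figure to reproduce first.

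**1. The rule, enumerated.** Inputs are from section 7.1.10.1: category maximum 0 to 3, with or without aids.

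| Category maximum | As written, no aid | As written, aid | 2 or above left unchanged, no aid | 2 or above left unchanged, aid |
|---|---|---|---|---|
| 0 | 0 | 2 | 0 | 2 |
| 1 | 1 | 2 | 1 | 2 |
| 2 | 2 | 2 | 2 | 2 |
| 3 | **2** | **2** | 3 | 3 |

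The two readings differ only at a score of 3.

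**2. Effect on the index.** Index = sum of category scores / 8 when all categories are answered.

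- Maximum as written: 8 × 2 / 8 = 2.0. Maximum with 3 retained: 8 × 3 / 8 = 3.0.
- One category from 3 to 2: true change 1/8 = 0.125; as written 0.
- One category from 3 to 1: true change 2/8 = 0.25; as written 1/8 = 0.125. It is halved, not erased.
- Two categories from 3 to 2: true change 0.25, which meets 0.22; as written 0.
- All eight from 3 to 2: true change 3.0 − 2.0 = 1.0 (33.3%); as written 0.

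**3. Effect on the ACR20 component (improvement of at least 20%).** Misclassification can go either way, because the cap lowers the baseline as well as the change.

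- Four categories go from 3 to 2 and four stay at 2. True: the sum falls from 20 to 16, 4/20 = 20%, met. As written: 16 to 16, 0%, not met.
- Six categories stay at 3 and two go from 2 to 0. True: 22 to 18, 4/22 = 18.2%, not met. As written: 16 to 12, 4/16 = 25%, met.

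**4. Illustrative effect on the treatment comparison.** The documents give no share of categories at 3, so this is an assumption, shown over a range. Eight categories (0 to 3) were simulated with subject-level means of 1.5, 1.8 and 2.1, with and without a cap at 2.

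| Assumed baseline share at 3 | Difference, uncapped | Difference, capped | Reduction | Standardised effect, uncapped to capped | Reduction |
|---|---|---|---|---|---|
| 15% | 0.250 | 0.207 | 17% | 0.52 to 0.51 | 2% |
| 24% | 0.261 | 0.199 | 24% | 0.53 to 0.50 | 6% |
| 34% | 0.260 | 0.177 | 32% | 0.53 to 0.47 | 11% |

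**5. What that does to power.** Take 140 per arm, 1-sided alpha 0.0125 (critical value 2.241) and a normal approximation: power = Φ(d × √(140/2) − 2.241), with √70 = 8.367.

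- d from 0.52 to 0.51: Φ(2.11) = 98.3% to Φ(2.03) = 97.9%.
- d from 0.53 to 0.50: Φ(2.19) = 98.6% to Φ(1.94) = 97.4%.
- d from 0.53 to 0.47: Φ(2.19) = 98.6% to Φ(1.69) = 95.5%.

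The loss is about 0.4 to 3 percentage points for this test.

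**The case against.** The strongest reply is that this is an obvious slip. A score of 3 cannot *remain* 2, the sentence is really about whether aids alter a score, and the 0 to 3 scale shows what was meant. Section 9.4 leaves analysis details to an SAP finalised before unblinding, and the documents contain no separate HAQ-DI scoring section, so it is not shown that the analysis will truncate. Item scores are collected, so nothing would be lost. The consequences may also be small:

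- The power loss above is modest even at the highest assumed share.
- The all-3s subject is extreme, given the class IV exclusion.
- HAQ-DI is one of five measures of which three are needed for ACR response.
- The 0.22 responder endpoint is outside the alpha-controlled sequence.
- The rule applies equally to all arms, and no inflation of type I error is claimed.

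Most of this stands as a limit on size. The slip is the likely explanation, the raw 17% to 32% shrinkage overstates the effect on the test, and no effect on ACR response rates has been quantified. It does not remove the defect. This is the only HAQ-DI scoring rule in the documents, and the only value it gives is the wrong one for the scale. Leaving it means an analyst must choose how to derive a confirmatory endpoint when the data are programmed. The two examples in step 3 also show that the cap is not reliably conservative for the ACR component.

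**Conclusion.** The concern holds. As written, the rule contradicts the 0 to 3 scale in the same section, caps the index at 2.0 instead of 3.0, scores every 3-to-2 category change as 0 instead of 0.125, and halves every 3-to-1 change. These results are arithmetic on the stated rule and need no assumptions.

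The size in the trial does rest on assumptions. It is nil if no category is scored 3 and grows with the share that are. The ranges in steps 4 and 5 illustrate the scale of loss under assumed shares and effects; they are not estimates for this trial. Correction is warranted because the rule defines an alpha-controlled endpoint that gates two others and enters the primary composite.

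**What to change.** In section 7.1.10.1, replace the sentence with: *If the category score is already 2 or 3, it is left unchanged, with or without aids, devices or help.*

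Carry the same rule into the SAP and the derived-dataset specification, so that it governs the HAQ-DI change, the 0.22 responder endpoint, the percent-improvement curve and the HAQ-DI component of ACR20/50/70. Confirm before unblinding that the analysis program returns 3 for a category whose highest item is 3.

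The cost is one sentence and one programming check. Nothing changes in data collection, sample size or the testing sequence.

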7.1.10.2 Short Form-36

The SF-36 health survey is a patient-reported survey of health; it is commonly used in health economics as a variable in the quality-adjusted life year (QALY) calculation to determine the cost-effectiveness of a health treatment. The SF-36 consists of 8 scaled scores, which are the weighted sums of the questions in their section. Each scale is directly transformed into a 0 to

100 scale on the assumption that each question carries equal weight. The lower the score the more disability. The higher the score the less disability (i.e., a score of zero is equivalent to maximum disability and a score of 100 is equivalent to no disability).

The 8 domains of the SF-36 are as follows:

- Vitality
- Physical functioning
- Bodily pain
- General health perceptions
- Physical role functioning
- Emotional role functioning
- Social role functioning
- Mental health

7.1.10.3 European Quality of Life – 5 Dimensions

The conceptual basis of the EQ-5D is the holistic view of health, which includes the medical definition and the fundamental importance of independent physical, emotional, and social functioning. The concept of health in EQ-5D also encompasses both positive aspects (well-being) and negative aspects (illness).

The EQ-5D consists of a questionnaire and a VAS and is a self-rated health status. The EQ-5D records the subject's perceptions of their own current overall health, and can be used to monitor changes with time. The self-assessment questionnaire is a description of the 5 dimensions (i.e., mobility, self-care, usual activities, pain/discomfort, and anxiety/depression). The subject is asked to grade their own current level of function in each dimension into 1 of 5 degrees of disability (extreme, severe, moderate, slight, or none). The combination of these with the conditions "death" and "unconscious" enables description of 3127 different health states. Each health state can be ranked and transformed as a single score called the utility.

The EQ-5D health states may be converted into a single summary index by applying a formula that attaches values to each of the levels in each dimension. The index can be calculated by deducting the appropriate weights from 1, the value for full health (i.e., state 11111). Value sets have been derived for EQ-5D in several countries using the European

Quality of Life-5 Dimensions Visual Analog Scale (EQ-5D VAS) valuation technique or the time trade-off valuation technique.

7.1.10.4 Work Productivity Survey – Rheumatoid Arthritis

The WPS-RA measures the impact of RA and treatment on subject productivity within and outside the home during the previous month. It contains 9 questions addressing employment status, productivity within and outside the home, and daily activities. One item of the WPS-RA addresses current labor market participation. This is a strong indicator of work ability because not working implies complete loss of paid productivity. There are also normative and comparative data available on employment status. Two items capture self-reported work absences due to arthritis, and 2 items capture the same concept but applied to non-paid work. These are separated into full and partial days (i.e., days of work missed and days with productivity reduced by at least half). Additional items capture the respondent's estimate of the extent to which arthritis has interfered with the subject's work productivity (paid and non-paid) on a scale of 0 to 10, the number of days in the last month outside help was hired because of arthritis, and the number of days in the last month family, social, or leisure activities were missed because of arthritis.

7.1.10.5 Functional Assessment of Chronic Illness Therapy – Fatigue Scale

FACIT-Fatigue is a 13-item tool that measures an individual's level of fatigue during their usual daily activities during the most recent week. The level of fatigue is measured on a 4-point Likert scale.

The sum of the scoring (total score) will be used for the statistical evaluation. If an item is not scored, the total score will be set to missing.

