4.3 Other Efficacy Endpoints

The following additional efficacy endpoints will be used to compare OKZ with placebo:

- Proportion of subjects achieving an ACR20, ACR50, and ACR70 response and remaining on randomized treatment and in the study, assessed at all other applicable time points
- Proportion of subjects with Simplified Disease Activity Index (SDAI) ≤ 3.3 (remission) and remaining on randomized treatment and in the study, assessed at all applicable time points
- Proportion of subjects with CDAI ≤ 2.8 (remission) and remaining on randomized treatment and in the study, assessed at all other applicable time points.
- Proportion of subjects with DAS28 low disease activity (based on DAS28 [CRP] <3.2) and remaining on randomized treatment and in the study, assessed at all other applicable time points

- Proportion of subjects with improvement from baseline in HAQ-DI score ≥ 0.22 and remaining on randomized treatment and in the study, assessed at all applicable time points
- Change from baseline over time in DAS28 (CRP)
- Change from baseline to Weeks 12 and 24 in DAS28 erythrocyte sedimentation rate (ESR)
- Change from baseline to all other applicable time points in the measure of physical ability (HAQ-DI)
- Change from baseline to Weeks 12 and 24 in the scores for the following patient-reported outcome (PRO) measures:
 - Short Form-36 (SF-36) Physical Component Summary (PCS) and Mental Component Summary (MCS) total scores
 - European Quality of Life-5 Dimensions (EQ-5D)
 - Work Productivity Survey-Rheumatoid Arthritis (WPS-RA)
 - Functional Assessment of Chronic Illness Therapy – Fatigue Scale (FACIT-Fatigue)
- Change from baseline to all applicable time points in SDAI and CDAI
- Proportion of subjects with moderate to good responses for EULAR based on DAS28 (CRP) and remaining on randomized treatment and in the study, assessed at all applicable time points, where a moderate response is defined as either DAS28 (CRP) ≤ 5.1 with an improvement from baseline in DAS28 (CRP) > 0.6 and ≤ 1.2 , or DAS28 (CRP) > 3.2 with an improvement from baseline in DAS28 (CRP) > 1.2 , and a good response is defined as DAS28 (CRP) ≤ 3.2 with an improvement from baseline in DAS28 (CRP) > 1.2
- Change from baseline to all time points in the components of the ACR response criteria

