Contraceptive history/status	✓	✓	✓	✓	✓	✓	✓	✓	✓	✓	✓	✓	✓	✓	✓	✓	✓	✓
Concomitant and prior medications/non-drug therapy	✓	✓	✓	✓	✓	✓	✓	✓	✓	✓	✓	✓	✓	✓	✓	✓	✓	✓
Randomization		✓																
Study treatment allocation through IWRS		✓		✓	✓	✓	✓	✓	✓	✓	✓	✓	✓	✓				
Administer study treatment ^g		✓ ^h		✓	✓	✓	✓	✓	✓	✓	✓	✓	✓	✓				

Assessments ^a		Randomized Double-Blind Treatment Period														Safety Follow-Up Period		
Visit	1	2	3	4	5	6	7	8	9	10	11	12	13	14	15/EoT	SFU-1	SFU-2	SFU-3
Week	Screening	0/Baseline	1	2	4	6	8	10	12	14	16	18	20	22	24 (+2 ^b)	26 (+4 ^b)	30 (+8 ^b)	44 (+22 ^b)
Visit Window (days) for all subjects other than those included in the sample-rich PK subpopulation																		
	-28 to -1	±0	±2	±3	±3	±3	±3	±3	±3	±3	±3	±3	±3	±3	±3	±7	±7	±7
Prescribe rescue medication for nonresponders ⁱ										✓								
EFFICACY ASSESSMENTS																		
Patient Global Assessment of Disease Activity (VAS)		✓		✓	✓		✓		✓			✓			✓			
Patient Assessment of Pain (VAS)		✓		✓	✓		✓		✓			✓			✓			
HAQ-DI		✓		✓	✓		✓		✓			✓			✓			
SF-36, EQ-5D, FACIT-Fatigue, and WPS-RA		✓							✓						✓			
Joint counts (Independent Joint Assessment) ^j	✓	✓		✓	✓		✓		✓	✓		✓			✓			
Physician Global Assessment VAS		✓		✓	✓		✓		✓			✓			✓			
CRP	✓ ^k	✓		✓	✓		✓		✓			✓			✓	✓	✓	
ESR		✓							✓						✓			
LABORATORY/SAFETY ASSESSMENTS																		
AEs/SAEs ^l	✓	✓	✓	✓	✓	✓	✓	✓	✓	✓	✓	✓	✓	✓	✓	✓	✓	✓
IGRA	✓													✓				
HIV serology	✓																	
HBsAg, anti-HBs, anti-HBc, HCV Ab	✓																	
Pregnancy test ^m	✓	✓			✓		✓		✓		✓		✓		✓	✓	✓	✓

Assessments ^a		Randomized Double-Blind Treatment Period														Safety Follow-Up Period		
Visit	1	2	3	4	5	6	7	8	9	10	11	12	13	14	15/EoT	SFU-1	SFU-2	SFU-3
Week	Screening	0/Baseline	1	2	4	6	8	10	12	14	16	18	20	22	24 (+2 ^b)	26 (+4 ^b)	30 (+8 ^b)	44 (+22 ^b)
Visit Window (days) for all subjects other than those included in the sample-rich PK subpopulation																		
	-28 to -1	±0	±2	±3	±3	±3	±3	±3	±3	±3	±3	±3	±3	±3	±3	±7	±7	±7
INR, aPTT, fibrinogen ⁿ		✓			✓				✓						✓			✓
Lipid panel (fasting) ^o		✓			✓				✓						✓			✓
CV risk panel ^p		✓			✓				✓						✓			✓
HbA _{1c}	✓																	
Hematology ^q	✓ ^r	✓	✓		✓		✓		✓		✓		✓		✓		✓	✓
Chemistry panel ^s	✓ ^r	✓	✓		✓		✓		✓		✓		✓		✓		✓	✓
RF and anti-CCP	✓														✓			
Urinalysis ^t	✓	✓							✓						✓			✓
ANA and anti dsDNA antibody		✓													✓			✓
PG		✓ ^u																
Serum biomarkers related to targeted pathway		✓			✓				✓						✓			

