Missing data may also result from missed intermediate visits for subjects who completed the study. For all binary endpoints, missing intermediate responder status will be imputed from the surrounding visits. If the status at visits both before and after the missed visit is classified as responder, the subject will be considered a responder at the missed visit. Otherwise, the subject will be considered a nonresponder. If an assessment for a given binary endpoint at the last visit is missing for a completing subject, data from the 2 previous visits will be used with the same logic for determining the response status. For the ACR20/50/70 endpoints, if only some components of the response criteria are missing but the available components allow classifying the subject as a responder, the responder category will be used. Otherwise, the method based on surrounding visits as described above will be applied. Similarly, for all continuous endpoints, an average of values from the surrounding visits will be imputed for the missing visit.

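### One blank FACIT-Fatigue item out of 13 voids the total score; a proration rule would keep almost all of those forms

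*Combined protocol and SAP*

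**What the plan says.** Section 7.1.10.5 describes the instrument ("FACIT-Fatigue is a 13-item tool") and the score to be analysed: "The sum of the scoring (total score) will be used for the statistical evaluation". It then gives the missing-item rule: "If an item is not scored, the total score will be set to missing". It has no proration and no minimum number of answered items.

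Section 4.3 lists FACIT-Fatigue among the other efficacy endpoints, under "Change from baseline to Weeks 12 and 24 in the scores for the following patient-reported outcome (PRO) measures". In Table 1 the row "SF-36, EQ-5D, FACIT-Fatigue, and WPS-RA" is marked at baseline, Week 12 and Week 24 only.

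For intermediate missing data, Section 9.4.9.1 says that "for all continuous endpoints, an average of values from the surrounding visits will be imputed for the missing visit". The paragraph is introduced as dealing with missed visits in subjects who completed the study.

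The HAQ-DI is scored more tolerantly. Section 7.1.10.1 divides the sum of the category scores by the number of categories answered, and adds: "If fewer than 6 categories have responses, no disability score will be calculated".

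**The concern.** A single skipped item removes twelve answered ones from the analysis. Those twelve answers are the best available evidence of the subject's fatigue at that visit. Whatever replaces them, whether nothing or a value built from visits 12 weeks away, is less informative.

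Two things are at stake. The first is precision: the rule applies at each of the three visits, and a change score needs two of them. The second is possible bias. If the neighbouring-visit average is used, the only FACIT-Fatigue values around Week 12 are baseline and Week 24. The filled-in Week 12 change is then half the Week 24 change, whatever the subject reported at Week 12. Under Section 9.4 that Week 24 value may also have been recorded after rescue medication began.

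**Working it through.** **Plan's own figure.** There is none to reproduce: the documents give no item non-response rate and no expected loss for FACIT-Fatigue.

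**Inputs.** From the documents: 13 items and the any-blank rule (Section 7.1.10.5), 140 subjects per arm (Section 9.1), assessments at baseline, Week 12 and Week 24 (Table 1), and the averaging rule (Section 9.4.9.1). Assumed: each item is blank with probability q = 0.5%, 1% or 2%, independently of the others and equally in all arms.

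**Step 1: totals lost per visit.** P(total missing) = 1 − (1 − q)^13. The share of lost forms with exactly one blank is 13q(1 − q)^12 / [1 − (1 − q)^13].

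| q | Totals lost | Expected number of 140 per arm | Lost forms with exactly one blank |
|---|---|---|---|
| 0.5% | 6.3% | 8.8 | 97% |
| 1% | 12.2% | 17.1 | 94% |
| 2% | 23.1% | 32.3 | 88% |

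Most of the discarded forms therefore have 12 of 13 answers.

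**Step 2: if the averaging rule does not apply.** The form is lost. For a comparison restricted to subjects with a Week 12 total, the standard error grows by 1/√(1 − loss):
- 1/√0.937 = 1.03
- 1/√0.878 = 1.07
- 1/√0.769 = 1.14

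A Week 12 change also needs a baseline total, and Table 1 has no Screening FACIT-Fatigue to fall back on. The chance that at least one of the two totals is blank is 1 − (1 − q)^26 = 12%, 23% and 41%, if blanks are also independent between visits.

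**Step 3: if the averaging rule does apply.** Imputed Week 12 change = (baseline + Week 24)/2 − baseline = half the Week 24 change. Let r be the true Week 12 treatment effect divided by the true Week 24 effect. An imputed total then carries 0.5/r of the true Week 12 effect: 0.50 at r = 1, 0.67 at r = 0.75 and 1.00 at r = 0.5. The attenuation of the Week 12 treatment difference is loss × (1 − 0.5/r):

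| Loss | r = 1 | r = 0.75 | r = 0.5 |
|---|---|---|---|
| 6.3% | 3.2% | 2.1% | 0 |
| 12.2% | 6.1% | 4.1% | 0 |
| 23.1% | 11.5% | 7.7% | 0 |

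The same formula gives more attenuation than the first column if the effect shrinks after Week 12 (r above 1), and inflation if r is below 0.5. It assumes that the baseline and Week 24 totals are themselves observed.

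**Step 4: what proration recovers.** The HAQ-DI fraction is 6/8; 13 × 6/8 = 9.75, so the matching threshold is 10 of 13 items. The chance of fewer than 10 answered items is 0.00004%, 0.0007% and 0.010% at q = 0.5%, 1% and 2%. With a threshold of 7 items it is smaller still (at most about 2 × 10⁻⁹). Under these assumptions either threshold recovers almost every lost form.

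**The case against.** The strongest objection concerns the imputation step. A reader might infer that the plan sends these forms into a biased imputation. The documents do not say so. The averaging rule is written for missed visits in completers, and a blank item at an attended visit is not a missed visit. The only provision there for partly missing data concerns the ACR components, and further detail is deferred to the SAP; the text reviewed contains nothing that settles the point. This objection stands, so the bias is conditional. The loss of the form is not.

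A reader might also take the 6% attenuation as a general result, or as proportional to item non-response. It is neither. It needs 12% loss and equal Week 12 and Week 24 effects, it disappears if improvement in the treatment difference is linear, and the loss itself is not linear in q.

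The skip rates are hypothetical. If blanks cluster within subjects, fewer totals are lost at the same item rate. Section 7.6.5.1 mentions site review of the questionnaires, and Section 8.1 has monitors check the eCRFs for completeness. Neither guarantees that a blank item is recovered, but both make the higher scenarios less likely.

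The HAQ-DI comparison is not a contradiction. The HAQ-DI is an average of category scores and FACIT-Fatigue is a sum, so different scoring rules can coexist. The comparison shows only that the protocol accepts partial data elsewhere. It does not support a 7-item threshold in particular.

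Finally, averaging with baseline, if used, would affect the SF-36, EQ-5D and WPS-RA as well, since they share the same three visits. Proration leaves that rule unchanged.

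**Conclusion.** The point holds as a minor improvement. The scoring rule is explicit and discards forms that are nearly complete. The expected loss is 6%, 12% or 23% of totals per visit at assumed independent item-blank rates of 0.5%, 1% or 2%, and less with clustering or querying.

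The consequence depends on a reading that the plan leaves open. Without imputation, the cost is precision. With the surrounding-visit average, 12% loss attenuates the Week 12 treatment difference by about 6%, 4% or 0% when the Week 12 effect is 100%, 75% or 50% of the Week 24 effect.

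FACIT-Fatigue is outside the multiplicity procedure of Section 9.4.6, so primary and secondary conclusions, power and sample size are untouched. The placebo-based imputation analysis in Section 9.4.9.2 covers only primary and secondary endpoints, so it would not show the effect of this rule on FACIT-Fatigue.

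**What to change.** Replace the missing-item sentence in Section 7.1.10.5 with a proration rule: total = sum of answered items × 13 / number answered, when a prespecified minimum is answered, and missing otherwise. The minimum can be more than half the items (at least 7) or, to match the HAQ-DI fraction, at least 10 of 13. The choice is the sponsor's and should be made before unblinding.

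Add one sentence on how a total that is still unscorable at an attended baseline, Week 12 or Week 24 visit is handled. The averaging rule does not literally cover this, and the two-previous-visits logic for a missing last visit is written for binary endpoints.

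The cost is two sentences and a line of programming, with no new data, visits or subjects. The downside is small: proration assumes that the skipped items resemble the answered ones.
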